### **Descriptive analysis of the data**

The data repository is structured in 6 tables: Inclusion, Baseline data, Procedure, Follow-up, Adverse event and Study exit. Summary information will be provided on the variables collected in each of the tables.

Regarding dates, the time elapsed between dates or waiting times will be calculated as specified by the scientific coordinators of the study.

### **Inclusion**

The Inclusion table contains sociodemographic information about the patient, the date of inclusion in the study, and the inclusion / exclusion criteria.

Continuous variables will be described using the statistics of central tendency (mean and median), dispersion (minimum, maximum, standard deviation and interquartile range) and shape (skewness and kurtosis). The number of valid cases and the number of cases with missing values will be reported. The continuous variables in this table are: Date of inclusion, Age, Weight and Height.

The categorical variables will be described by frequencies and percentages. The number of valid cases and the number of cases with missing values will be reported. The categorical variables contained in this table are: Sex, the inclusion criteria and the exclusion criteria.

## **Baseline data**

The Baseline Data table contains clinical information about the patient's situation at the baseline visit. Specifically, the date of the baseline visit, characteristics of AF, REDO, heart disease, risk factors, drugs, echocardiography, and lung anatomy.

Continuous variables will be described using the statistics of central tendency (mean and median), dispersion (minimum, maximum, standard deviation and interquartile range) and shape (skewness and kurtosis). The number of valid cases and the number of cases with missing values will be reported. The continuous variables in this table are: Date of the baseline visit, number of previous procedures, CHADS2 index, CHADS2DS2-VASc index, BMI, number of arrhythmic drugs, IVTDVI, IVTSVI and area and diameter of the LA dilatation.

The categorical variables will be described by frequencies and percentages. The number of valid cases and the number of cases with missing values will be reported. The categorical variables contained in this table are: AF type, AF evolution time, Associated arrhythmias, REDO, Type of previous procedure, Heart disease, Heart disease type, Channelopathy type, Congestive Heart Failure, Arterial hypertension, Age 65-74, Age  $\geq$  75 years, Diabetes Mellitus, Vascular disease, Female gender, History of stroke or Transient Ischemic Accident, Pacemaker carrier, Sports, Alcohol, SAHS, CPAP, Dyslipidemia, Obesity, Antiarrhythmic drugs, Type of antiarrhythmic agents, Beta-blockers, Calcium antagonists, Anticoagulants, Type anticoagulants, NACOs Type, FE, Ventricular Dilation, AI Dilation, VPI, VPI Type, VPD, VPD Type.

## **Procedure**

The Procedure table contains technical information about the ablation procedure.

Continuous variables will be described using the statistics of central tendency (mean and median), dispersion (minimum, maximum, standard deviation and interquartile range) and shape (skewness and kurtosis). The number of valid cases and the number of cases with missing values will be reported. The continuous variables in this table are: Procedure date, TTE (sg), Minimum temperature ( $^{\circ}$ C), Application time (sg), Reheating time (sg), No. of balloons used, Total time of applications (min), Time total LA (min), Total procedure time (min), Total fluoroscopy time (min), Time to -30 degrees (sec), Rx Dose (PDA), Wait time (min), Contrast (ml), No. of cardioversions.

The categorical variables will be described by frequencies and percentages. The number of valid cases and the number of cases with missing values will be reported. The categorical variables contained in this table are: Study No., Previous Image, Image Type, Previous TEE (Transesophageal Echocardiography), General Anesthesia, Deep Sedation, Channeled Artery, No. of Diagnostic Catheters, Location of Diagnostic Catheters, Access, Assisted Transeptal, Assisted using, Phrenic nerve monitoring technique, Base rhythm, Applications, Vein, Application number, Potential visibility, Balloon size, Pulmonary vein isolation, Auriculogram, Protamine, Z-suture, Complications, Cardioversions, Number of cardioversions, Ablation ICT, Post-procedure antiarrhythmics, Antiarrhythmic type, Post-procedure anticoagulation, NACOs type, Base rhythm, Select type of Flutter, Catheter, Sheath, Specify.

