#### 4.2. Device information

The Arctic Front Advance® connected to a nitrous oxide conveying system is used for pulmonary vein cryoablation which is inserted through a steerable sheath (FlexCath Advance®). The system progresses to the pulmonary vein ostium through a single transseptal catheterization and the balloon impacts against the venous ostium. When the nitrous oxide circulating through the system in a liquid state is released into the inside of the balloon through 8 ejectors, it leads to the switch from a very high pressure system to a very low pressure system. The sudden decompression of nitrous oxide in a liquid state means that it is transformed into a gas, causing a powerful endothermic reaction that absorbs heat from the adjacent tissues (*Joule-Thompson effect*). This reaction is the basis of the lesion caused by cryotherapy. Aerated and reheated nitrous oxide returns to the console through a connected vacuum system. For the registration of pulmonary vein potentials in real time, a circular octapolar electrode catheter (AchieveTM) is used during the ablation with an interelectrode distance of 4-6 mm (depending on the diameter of the catheter) which is inserted through the lumen of the balloon. The special configuration of the AchieveTM catheter with a rigid proximal consistency 0.9 mm diameter high supporting guidewire, can be used as a supporting guidewire for the balloon on the one hand and as a mapping and stimulation electrode on the other.

Currently at least 2 applications of cryothermia through the pulmonary vein with a duration of 180 seconds are recommended. However, you need to keep in mind that the dosing recommendations are based on data from former investigational studies of focal cryoablation. It is obvious that none of the tissue properties, the technology, or the coolants that were used are the same as those used nowadays for pulmonary vein cryoablation. This has meant that, despite the recommended application parameters, new protocols have been trialled with shorter application times and a lower number of applications per vein. The reduction in the application times of cryothermia seems to also reduce some of the complications arising from the technique such as phrenic paralysis, a circumstance which occurs more frequently after the first minute of application and during extra application after the disconnection.

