#### **Baseline procedure:**

- 1.- Demographic factors, cardiovascular risk factors (arterial hypertension, diabetes mellitus, dyslipidemia, smoking), physical activity, sleep apnea, body mass index.
- 2.- Evolution time of the arrhythmia, previous anti-arrhythmic treatments, previous cardioversions.
- 3.- Anatomical data arising from the imaging tests (left ventricular parameters, ejection fraction, ventricular wall thickness, diameter, area or volume of the left atrium, pulmonary vein drainage pattern, pulmonary vein diameters)
- 4.- Procedure variables: number of applications per vein, application time, registration of pulmonary vein potentials during the ablation, time to block the vein, minimum temperature reached, reheating time, isolation or not of the pulmonary vein, results of the adenosine test, procedure time, exposure time to radioscopy, complications, temperature details in each of the applications, temperature at the time of isolation.

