# 13. Statistical design and methods

The following statistical analysis plan of the data will be carried out:

The variables analyzed will be those collected in the subject registry corresponding to the different protocols of the procedure, intervention data, complications, follow-up and long-term results in these subjects. In the Method section there is a list of variables of interest.

Recurrence of AF will be defined as a clinically diagnosed episode of AF and accordingly documented (on ECG, Holter monitor with a duration of at least 30 seconds or implantable devices or event recording systems).

It is expected to carry out 3 analyses of the primary and secondary objectives described in the Clinical Investigation Plan:

- 1. At the end of the first year of enrollment
- 2. At the end of the second year of enrollment
- 3. At the end of follow-up

On the other hand, there will be 4 analyses of additional proposals throughout the study (see Appendix B: Publications Plan)

- Two analyses at the end of enrollment.
- Two analyses at the end of follow-up.

Each of the variables of interest will be described univariantly and individually.

Crosses of variables will also be carried out to describe each one of the clinical strata of interest.

When it is possible and of interest for the investigators, statistical comparisons between strata will be carried out through statistical tests.

Specific statistical models to respond to the interests of the investigators will be proposed, such as comparison of the procedures or comparison of subject strata.

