### **Treatment of missing values**

The statistical analysis process assumes the correct monitoring of the data entry through the electronic data collection notebook. During the data analysis phase, no queries should be made to fill in missing information or missing values.

However, during the analysis process, missing and missing values will be identified for later treatment with the research team. Extreme and out-of-range values will also be identified for later review by the research team. The necessary corrections obtained from the identification of out-of-range values or missing information and reviewed by the patient's clinical manager will be entered into the database for subsequent treatment in subsequent re-analyses.

The initial data treatment strategy will be to assume a non-response as a completely random missing value (MCAR) and the treatment of missing values will be isolated by variable. If it is required to relate several variables in an analysis, the treatment will be "according to the pair" of variables considered (pairwise) to minimize the impact of the lost information on the estimates obtained.

In the cases in which the analysis of several consecutive measurements is carried out or the passage of time is valued, the carrying over of the last value obtained on subsequent measurements will be assumed. For example, if a subject has not suffered an event or there is no information on this aspect (missing value) at the time of closing the database, it will be assumed that the subject's status is the same as the last measurement with valid data.

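### An empty time-to-block value can mean that the vein had not blocked when the freeze ended, yet the SAP treats it as missing at random, so a naive comparison of protocols can favour the shorter freeze

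*SAP*

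**What the plan says.** Protocol section 9.1 (Baseline procedure) collects "time to block the vein, minimum temperature reached, reheating time, isolation or not of the pulmonary vein". The SAP's Procedure section has a matching run of continuous variables, "Procedure date, TTE (sg), Minimum temperature ( $^{\circ}$ C), Application time (sg), Reheating time (sg", with TTE directly before minimum temperature, where the protocol has time to block. The SAP never spells TTE out, so equating the two is an inference, though a reasonable one.

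For all these variables the SAP gives one recipe: "Continuous variables will be described using the statistics of central tendency (mean and median", together with range, SD, interquartile range and shape. It adds that "The number of valid cases and the number of cases with missing values will be reported". Potential visibility, application number and pulmonary vein isolation are tabulated as separate categorical variables and are not tied to TTE.

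The SAP's section on missing values says that the initial strategy is to "assume a non-response as a completely random missing value (MCAR) and the treatment of missing values will be isolated by variable". Variables analysed together are handled pairwise, and the last value is carried forward where consecutive measurements or the passage of time matter. Survival methods appear only under Statistical models, for time to AF recurrence.

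Protocol section 4.2 cites a 180-second application and says that "new protocols have been trialled with shorter application times and a lower number of applications per vein". Section 13 foresees models "such as comparison of the procedures or comparison of subject strata", and section 13.1 assigns Student's t test or analysis of variance to group differences in quantitative variables.

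**The concern.** Time to block is a time-to-event measurement with a built-in cut-off. If the application stops before block, all that is known is that the time is longer than the application time. An empty field then carries information: it marks a slow or failed vein. Dropping it as random removes the upper tail, and the point at which the tail is cut is the application time, which differs between protocols.

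The synopsis gives the study's purpose as reflecting practice across the different procedure protocols, with their details and results. A table of TTE by protocol would be a natural product of this registry. Under the stated rules, two protocols with the same distribution of block times could show different means and medians, and a t test could call the difference significant. Any TTE summary, compared or not, would also read as faster than the truth.

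**Working it through.** The documents give no TTE mean, SD or proportion without block, and the target of about 1000 subjects rests on procedure volume. There is no figure to reproduce, so the check tests the mechanism on stated assumptions.

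**Inputs**
- Freeze length 180 s: protocol section 4.2.
- Shorter freeze 120 s: assumption, for illustration only.
- True block times lognormal with median m and log-SD s, identical under both freezes: assumption. Range examined: m from 30 to 90 s, s from 0.5 to 0.9.
- A time is recorded only if block comes before the freeze ends: from the definition of the variable.

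**Formulas**, for freeze length c, with z = ln(c/m)/s and Φ the normal distribution function:
- share blocked: F = Φ(z)
- true mean: m·exp(s²/2)
- observed mean: true mean × Φ(z − s) / F
- observed median: m·exp(s·Φ⁻¹(F/2))

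**Worked case, m = 60, s = 0.8.** True mean = 60·exp(0.32) = 82.6 s.
- c = 120: z = 0.866, F = 0.807, Φ(0.066) = 0.5265. Observed mean = 82.6 × 0.5265/0.8069 = 53.9 s.
- c = 180: z = 1.373, F = 0.915, Φ(0.573) = 0.7168. Observed mean = 82.6 × 0.7168/0.9152 = 64.7 s.
- Spurious gap: 64.7 − 53.9 = 10.8 s. Observed medians are 49.3 and 55.1 s against a true 60 s.

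**Across assumptions** (120 s / 180 s)

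| m, s | No block by freeze end | Observed mean, s | Gap, s | Observed median, s |
|---|---|---|---|---|
| 30, 0.5 | 0.3% / 0.0% | 33.7 / 34.0 | 0.3 | 29.9 / 30.0 |
| 45, 0.7 | 8.1% / 2.4% | 47.4 / 53.0 | 5.6 | 41.9 / 44.1 |
| 60, 0.7 | 16.1% / 5.8% | 56.1 / 65.7 | 9.6 | 52.0 / 57.0 |
| 90, 0.7 | 34.1% / 16.1% | 67.4 / 84.2 | 16.8 | 66.1 / 78.1 |
| 90, 0.9 | 37.5% / 22.1% | 60.6 / 77.6 | 17.0 | 58.0 / 69.9 |

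The shorter freeze has the lower observed mean in every scenario. The gap grows with the share of veins that have not blocked by 120 s and all but disappears when that share is near zero. The median is shifted too.

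**False-positive rate.** Simulation with 500 independent applications per group, no true difference, 300 runs, nominal 0.05 (taken as two-sided):

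| m, s | t test on recorded TTE | Log-rank, censored at freeze end |
|---|---|---|
| 30, 0.5 | 9% | 7% |
| 45, 0.7 | 76% | 7% |
| 60, 0.7 | 98% | 6% |
| 90, 0.7 | 100% | 5% |

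Simulation error near the nominal level is about ±2.5 points, so the censored analysis stays close to 5%.

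**Visibility alone.** With the same 180 s freeze in both groups and potentials visible in 50% versus 80% of applications, unrelated to TTE, the t test rejects in 3% to 9% of runs, close to nominal.

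**Check on the remedy.** With every eligible application in the denominator, the proportion blocked by 60 s in the worked case is 50% under both freezes, and by 120 s it is 80.7% under both. Within a common horizon the artefact is gone.

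**The case against.** Several points on the other side are fair, and most of them stand.

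- **TTE is not the acute-efficacy measure.** A reader might infer that this undermines the acute-efficacy objective. It does not: protocol section 5.1.2 defines acute efficacy as complete isolation of the veins, and the SAP tabulates isolation with percentages. Veins that did not isolate are counted there. TTE is named in no objective.
- **No comparison by freeze length is planned.** A reader might conclude that the registry will report shorter freezes as faster. The documents support only that it could. Section 13 makes comparisons optional and leaves the models to be proposed.
- **The summary is not the mean alone.** Median, interquartile range and missing counts are also planned. This helps the reader but does not cure the problem, because the median moves too (52.0 versus 57.0 s at m = 60, s = 0.7).
- **The random-missingness rule is an initial strategy**, with missing values passed to the research team, and the case report form is not available. How TTE is coded when block fails is unknown; a blank is the natural reading but is not documented. The SAP nevertheless states no other rule for it.
- **Non-visible potentials** might seem to add to the bias. They do so in this comparison only if visibility is related to both TTE and protocol, which the documents do not say.
- **The size is assumed.** Only 180 s comes from the documents.
- **Censoring is not a complete answer.** Several veins per patient are not independent, and if freezes are stopped early because they perform poorly, censoring at application time is itself informative. The fix has to allow for both.

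**Conclusion.** The point holds for a procedural descriptor. A time-to-block value left empty because block did not occur is informative by definition, so the completely-at-random, variable-by-variable rule is the wrong default for TTE. Means and medians of recorded values are conditional on block within the application time and understate the true time.

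If protocols with different application times are compared on those values, the shorter freeze can look faster with no true difference. Under lognormal times with medians of 30 to 90 s and log-SDs of 0.5 to 0.9, and freezes of 120 versus 180 s, the spurious gap in means is about 0.3 to 17 s. It is negligible if nearly all veins block early, and the documents do not show where this registry lies in that range.

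The conclusion assumes that TTE is the time to block and that the field is empty when block fails. It does not touch the primary endpoint or the acute-efficacy objective, and it does not show that a misleading comparison will be made. It is still worth acting on, because the default is wrong in a known direction and the remedy uses fields already collected.

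**What to change.** Add one paragraph to the SAP's Procedure section:

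1. Define TTE and its unit: the first application to each vein, with conduction present at the start and potentials visible.
2. Exempt TTE from the completely-at-random and carry-forward rules.
3. Count applications that ended without isolation, those with potentials not visible, and those on an already isolated vein as separate categories, apart from truly missing values.
4. Report the proportion blocked by fixed times (for example 60 s and 120 s, as reporting times only) within a horizon common to the protocols compared, with a Kaplan-Meier estimate censored at the application time.
5. Base any comparison between protocols on these quantities and not on Student's t, and allow for several veins per patient.
6. State that censoring may be informative if freezes are stopped early for poor performance.

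Treating the time to −30 degrees in the same way is optional; it was not examined here.

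Cost: one paragraph. Application number, potential visibility, isolation and application time are already in the Procedure table, and the SAP already uses Kaplan-Meier for recurrence. The reported times will be longer and look less favourable. Nothing about how the freeze is carried out needs to change.

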## **Follow-up**

The Follow-up table contains clinical information related to the follow-up of the patient. At the time of writing this protocol, it is unknown whether a patient can have multiple follow-up visits.

Continuous variables will be described using the statistics of central tendency (mean and median), dispersion (minimum, maximum, standard deviation and interquartile range) and shape (skewness and kurtosis). The number of valid cases and the number of cases with missing values will be reported. The continuous variables in this table are: Date of the follow-up visit, Date of post-procedure discharge, Date of admission, Date of discharge, Number of hospital stays.

The categorical variables will be described by frequencies and percentages. The number of valid cases and the number of cases with missing values will be reported. The categorical variables contained in this table are: Follow-up visit, ECG record / Monitoring type, Recurrence 3 months post-procedure, Recurrence specification, Asymptomatic AF, Treatment, Antiarrhythmics, Antiarrhythmic type, Specify, Anticoagulants, NACOs type, REDO, Type REDO, Death, Hospital stay

### **Adverse event**

The Adverse Event table contains clinical information regarding adverse events that occurred during patient follow-up. It is assumed that a patient may experience several (or none) adverse events during follow-up. Therefore, two types of descriptive analysis will be carried out, one using the number of patients as the unit of analysis (summarizing aspects such as the number of events per patient, maximum and minimum time between events, etc.) and another using the units of analysis as reported events (to summarize aspects such as the most frequent type of event, the most frequent level of severity, resolution of the events, etc.)

Continuous variables will be described using the statistics of central tendency (mean and median), dispersion (minimum, maximum, standard deviation and interquartile range) and shape (skewness and kurtosis). The number of valid cases and the number of cases with missing values will be reported. The continuous variables in this table are: Date of the adverse event, Date of knowledge of the EA, Date of resolution.

The categorical variables will be described by frequencies and percentages. The number of valid cases and the number of cases with missing values will be reported. The categorical variables contained in this table are: Type of event, event (s), Type of complications, event (s), Type of arrhythmia, Is the AE serious ?, Type of severity, Measures taken, Status of the event.

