#### Annual follow-up (+/- 28 days):

5.- Variables during follow-up: anti-arrhythmic treatment, clinical recurrence of arrhythmia, result of the continuous ECG monitoring, 12-lead ECG, Nuubo monitoring method, etc. according to the protocol for each site.

A blanking period of 3 months has been established.

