#### 9.6. Safety assessment

The products used have the CE mark and are used under the authorized indications for use according to their label. However, it is the investigator's responsibility to comply with any requirements for the reporting of Adverse Events (AE) as required by the Clinical Investigation Plan, by local legislation, and the specific requirements of each EC.

The investigators of this registry will report any deficiencies/malfunction and any adverse events related to the medical device through the regular channel from the vigilance system. As part of Medtronic's continual post-marketing safety assessment, Medtronic will evaluate those experiences and events and will produce monitoring reports for the local competent authorities as required.

In this registry, the adverse events will be reported through the eCRF. The investigator must enter all the information on the eCRF as soon as possible and before 10 calendar days from awareness date of the event, as long as the regulatory authorities do not require stricter timelines.

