## 11.2. Adverse Event and Device Defficiency reporting

The investigators of this registry will report any deficiencies/malfunction and any adverse events related to the medical device through the regular channel from the vigilance system. As part of Medtronic's continual post-marketing safety assessment, Medtronic will evaluate those experiences and events and will produce monitoring reports for the local competent authorities as required.

The investigator must notify the sponsor or its representative and the reviewing EC of any unexpected adverse event of the device, within 24 hours from awareness date.

In this registry, the adverse events will be reported through the eCRF. The investigator must enter all the information on the eCRF as soon as possible and before 10 calendar days from awareness date of the event, as long as the regulatory authorities do not require stricter timelines.

The following adverse events will be collected in this registry:

- Unanticipated Serious Adverse Device Events (USADE):
- All adverse events that lead to death.
- All adverse events related to the procedure (up to 30 days post-procedure), such as (non-exhaustive list):
  - Access site complications:
    - Arteriovenous fistula
    - Pseudoaneurysm
  - Endocarditis
  - Cardiac damage (including myocardial infarction)
  - Embolic complications (including stroke)
  - Tamponade (associated or not to urgent surgery)
  - Hemorrhage requiring transfusion
  - Temporal Paralysis of the phrenic nerve

Version 1.0 11/APR/2016

- Persistent Paralysis of the phrenic nerve
- Pulmonary vein stenosis
- Intense cephalea
- Hemoptysis
- Gastroparesis
- Mitral valve tearing
- Temporary STU elevation

Note: Early recurrences of AF/AFL/AT after the cryoablation process are to be expected. If these recurrences, which may require hospitalization of the subject or extension of his/her hospitalization, are within the "blanking" period, they will not be considered greater complications than the cryoablation procedure.

Note 2: temporal paralysis of phrenic nerve is defined as decrease in diaphragmatic excursion resolved prior to end of procedure. Detection of phrenic nerve damage prior to detectable decrease in diaphragmatic excursion during procedure will not be considered as AEs.

- All adverse events related to AF not related to the procedure (that appear after 30 days, throughout the study), which could be (non-exhaustive list):
  - Cardiovascular death
  - Systemic embolism

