## 13.1. Analysis of clinical data

It is expected to include approximately 1000 subjects enrolled at approximately 30 Spanish sites, with an enrollment period of 2 years and a follow-up period of one year from the time of enrollment of each subject. The subjects analyzed will be the ones included in the RECABA study database: "Spanish Registry of Cryoballoon Ablation". The variables analyzed will be those mentioned previously with the intention of adequately describing the activity of the clinical sites, the procedures used and the diseases treated in accordance with standard clinical practice.

All the data are anonymized in origin so that it is not possible to identify the subjects.

The collection of data will be prospective from the time of enrollment.

The database will be received codified and debugged, and the allocation of the lost values that have been decided previously.

The basic report at the end of enrollment and at the end of the follow-up period will consist of: The quantitative variables are expressed as mean, median, typical deviation and interquartile range depending on which is most suitable for the distribution of values. The differences between groups in relation to the quantitative variables will be evaluated through the student t test for independent samples or the analysis of variance (depending on the number of groups compared) and between variables through the student t test for related samples or the analysis of variance of repeated measures, as applicable. To analyze the relationships between categorical variables the chi-squared test ( $\chi^2$ ) and the Fisher's exact test will be used. The differences of proportions will be assessed through the homogeneity test  $\chi^2$ . To assess the relationships between the quantitative variables the Pearson or Spearman r correlation will be used, as appropriate.

The intermediate statistical reports proposed by the investigators will depend on the hypotheses suggested by the investigator. They will include at least a descriptive analysis such as the one described previously. In addition, the appropriate models to respond to the hypotheses proposed will be estimated, which can include techniques of the style of exploratory factor analysis, analysis of multiple contingency, analysis of logistical regression, analysis of conglomerates or analysis of multifactorial variance.

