### **Study exit**

The Study Exit table contains clinical information regarding the patient's study exit.

This table only contains two variables: the reason for leaving and the date of departure. Both variables will be adequately described by frequency of the reasons and the calculation, for their description and summary, of the corresponding waiting times.

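### Late AF-related events other than recurrence get crude counts with no exposure measure or fixed window, so the end-of-enrolment figures mix unequal follow-up

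*SAP*

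**What the plan says.** Protocol 11.2 sets two collection periods for adverse events. Procedure-related events run to day 30. The second group is open-ended: "All adverse events related to AF not related to the procedure (that appear after 30 days, throughout the study"). Its examples include cardiovascular death, systemic embolism, heart failure, bleeding, infarction and stroke, together with flutter, inappropriate sinus tachycardia and sinus dysfunction once the blanking period is over. Recurrence of AF is recorded on the same form but analysed as efficacy.

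The SAP's Adverse event section describes these data per patient, "summarizing aspects such as the number of events per patient, maximum and minimum time between events, etc", and per event, with frequencies and percentages for the categorical fields. Its date fields are "Date of the adverse event, Date of knowledge of the EA, Date of resolution". No denominator in patient-time, cumulative incidence or fixed window is named. In the SAP's Statistical models section, the 12-month time point and Kaplan-Meier are given for AF recurrence only.

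Protocol 13.1 gives each subject one year of follow-up and specifies the report at two times: "The basic report at the end of enrollment and at the end of the follow-up period will consist of" the descriptive statistics and tests listed there. The Synopsis and section 6.1 allow follow-up to be extended.

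On when an event becomes known, the protocol schedules an "Annual follow-up (+/- 28 days") visit. Entry of an event is due "as soon as possible and before 10 calendar days from awareness date of the event" (section 9.6), so the clock starts at awareness and not at the event itself.

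**The concern.** At the end of a two-year enrolment period, about half the subjects would have less than 12 months of observation, and a few would not yet have passed day 30. A count or a mean number of events per patient over everyone enrolled then measures follow-up as well as risk. A reader who sets that report beside the final one, or beside a published 12-month series, could take shorter observation for a lower late risk of stroke or bleeding. If follow-up were later extended with no 12-month limit, the final figures would err in the other direction. The SAP deals with incomplete observation for AF recurrence but not for these events.

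**Working it through.** The documents give no late-event rate, so there is no planned figure to reproduce. The check is on observation time.

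**Inputs from the documents.** About 1000 subjects; 2 years of enrolment; 1 year of follow-up per subject; late events start after day 30; visit window of 28 days; blanking period of 3 months. **Assumptions.** Procedure on the enrolment date; even accrual unless stated; constant event rate after day 30. Under a constant rate, the mean number of late events per patient is proportional to mean late time. The percentage of subjects with an event follows it closely when risks are low.

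**End of enrolment, one-year limit.** Let d = 30/365 = 0.0822 years.
- Full late time per subject: 1 − d = 0.9178 years.
- Half the subjects have all of it. The other half average (1 − d)²/2 = 0.4212.
- Mean: (0.4212 + 0.9178)/2 = 0.6695. Ratio: 0.6695/0.9178 = **0.73**.
- If accrual rises linearly from zero, the ratio is 0.55. If it falls linearly to zero, it is 0.91.
- For events that count only after 3 months: (0.75²/2 + 0.75)/2 = 0.5156, and 0.5156/0.75 = 0.69.

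For an assumed true 1, 2 or 4 events per 100 subjects by month 12, the crude figure at 73% would be 0.7, 1.5 or 2.9.

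**Extreme case of late reporting.** Suppose no late event is known before the annual visit. With the visit at day 365, half the subjects have been seen and the ratio is 0.50. With the visit at day 393, (2 − 393/365)/2 = 0.46. A patient-time rate over all subjects up to the cut-off does not fully repair this: 0.50 × 0.9178/0.6695 = 0.685 and 0.4616 × 0.9178/0.6695 = 0.633, so the rate would be 31% to 37% too low.

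**End of enrolment, no one-year limit.** If early subjects go on being observed and events are known at once, mean late time is (2 − d)²/4 = 0.9195 years against 0.9178. The ratio is 1.00, but this is a coincidence of even accrual.

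**Final report.**
- One-year limit, no dropout: 1.00. With a share p of dropouts spread evenly over the year, the ratio is (1 − p) + 0.459p: 0.97 at 5% and 0.95 at 10%.
- Follow-up extended for all to a common close at month 36: (2 − d)/(1 − d) = 2.09, with late time running from about 11 to 35 months.

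**Procedure complications.** At the end of enrolment about 1000 × (30/365)/2 = 41 subjects have under 30 days. If half of the complications fall on day 0 and the rest evenly over days 1 to 30, the crude percentage is 1 − 0.041 × 0.5 × 0.5 = 0.99 of the true one.

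**Start of time at risk.** Counting from day 31 for arrhythmias that qualify only after 3 months would put 0.918 years in the denominator where 0.75 belongs, about 22% too much.

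**The case against.** The SAP's list is illustrative and open-ended. Its Descriptive analysis section leaves elapsed times to the coordinators, and its Study exit section already plans "the calculation, for their description and summary, of the corresponding waiting times". That is fair: time on study is partly described. It is not used as a denominator for events, and an analysis left to later discretion is not yet a plan.

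The SAP does not ask for a percentage of subjects with a late event. Its percentages describe fields of the event form, and it does not split the table at day 30. This also stands. The planned item that unequal follow-up affects directly is events per patient; the per-100 figures above are what a reader would derive from the counts.

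The shortfall depends on a one-year limit. With that limit the final report already has a nearly common window; without it, the end-of-enrolment shortfall can vanish. Both statements are correct, so the 73% is conditional. What remains in either case is that the exposure behind the figure is undefined.

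Reporting delay may be small. Table 1 of the protocol has adverse events recorded as they happen, and the SAP's Follow-up section says it is not known whether a patient can have several visits. A stroke or infarction will often reach the site before the annual visit. The 46% to 50% is therefore a bound and not an expectation.

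Finally, the gain is modest. At an assumed 2% risk, a crude 15 of 1000 has a 95% interval of 0.8% to 2.5%, which includes 2.0%, and stating median follow-up beside the counts would prevent much of the misreading. That argues for a small fix; it does not remove the point.

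**Conclusion.** The gap is real and small. Late AF-related events other than recurrence are collected over an open period and summarised without exposure or a fixed window. With one year per subject, even accrual and a constant rate, the end-of-enrolment figure would be about 73% of the 12-month one. Accrual shape moves this between 55% and 91%, and delayed reporting could lower it further. Under the same limit the final report is nearly right. An extension is permitted but not decided.

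Three stronger readings are not supported.
- A reader might infer that the interim late-event figure will be about half the true one. That needs every event to stay unknown until the annual visit, which no document says.
- A reader might infer that subjects without information will be counted as event-free, because the SAP's missing-value section says "it will be assumed that the subject's status is the same as the last measurement with valid data". That rule is written for consecutive measurements or the passage of time, and nothing applies it expressly to these events.
- A reader might infer that the study's conclusions are at risk. No listed objective or hypothesis rests on these events: procedure complications have a 30-day window, and AF recurrence has its own analysis.

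This is an optional improvement to descriptive late-safety reporting.

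**What to change.** In the SAP's Adverse event section, keep the raw counts. For late AF-related events other than AF recurrence, add at the end-of-enrolment and final reports:

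1. Total patient-years and median follow-up, measured from the procedure date.
2. The 12-month cumulative incidence of a first late event with death as a competing event, or first events per 100 patient-years with an exact 95% interval.

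Start time at risk at day 31 for stroke, embolism, heart failure, bleeding, infarction and cardiovascular death. Start it at the end of the 3-month blanking period for flutter, inappropriate sinus tachycardia and sinus dysfunction. End it at the earliest of first event, study exit, last contact for subjects lost to follow-up, data cut-off, or day 365.

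At the end of enrolment, show the same estimate in subjects whose procedure was at least 393 days (365 + 28) before the cut-off, as a check for late reporting. Select them by procedure date alone. Adding later-treated subjects because they had an event or left early would over-represent events and deaths. Keep crude percentages for 30-day procedure complications.

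The cost is SAP wording, a little programming and one extra table; the procedure, event, knowledge, visit and exit dates are already collected. The restricted interim estimate is less precise. Under even accrual it would hold about 462 of 1000 subjects and 462 × 0.9178 = 424 late patient-years, where 9 events give 2.1 per 100 patient-years (95% interval 1.0 to 4.0). At the final report, 20 events in 918 patient-years would give 2.2 (1.3 to 3.4). The event numbers are illustrative.
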